5.2.1. Intercurrent Events (ICEs) and Early Escape (EE)

Tabulations by randomized intervention group will also be provided for participants who met EE criteria at Week 16 and for participants who met 1 or more ICEs for the Adjusted Composite Estimand prior to Week 24 as defined in Section [5.3.4.2](#).

Listings of participants who met any ICE criteria will be presented.

5.3. Efficacy Analyses

5.3.1. General Method of Analysis

In general, descriptive statistics, such as mean, standard deviation (SD), median, inter quartile (IQ) range, minimum, and maximum for continuous variables, and counts and percentages for discrete variables will be used to summarize most data.

Statistical comparison between a guselkumab group (100 mg q4w or 100 mg at Weeks 0, 4 and then q8w) and the placebo group will be performed by visit through Week 24. No treatment comparison will be performed after Week 24.

Binary Response Efficacy Endpoints

For binary response efficacy endpoints where any portion of the missing data is imputed using Multiple Imputation (MI) (see Section 6.11 for technical details), treatment comparisons will be performed using a Cochran-Mantel-Haenszel (CMH) on each of the imputation sets, and the inferences from the analysis of each imputed data are pooled. The within imputation variance and between imputation variance are combined to estimate the total variance of the stratum adjusted difference of proportions. This estimate of the variance and critical values from the t-distribution are used to calculate the confidence interval for the stratum adjusted difference of proportions. The SAS procedure PROC MIANALYZE is used where the critical value is based on the t-distribution which is different from the analysis not based on MI where normal distribution is used. The large number of observations in our data imply that the critical values from the t-distribution are almost identical to the critical values from the standard normal distribution. The Wilson-Hilferty (Ratitch 2013) transformation is used to pool the CMH statistics from each imputed data set to calculate the p-value.

For analyses where all missing data is imputed only a single time (e.g., non-responder imputation for all missings) or not imputed with the missing assumed Missing Completely at Random (MCAR), treatment comparisons will generally be performed using a CMH test. The magnitude of the treatment difference will be estimated by the difference in response rates between the guselkumab and placebo groups with a 95% confidence interval (CI) calculated based on Wald statistics (Yeonhee 2013). The Mantel Fleiss criterion will be used to determine the appropriateness of using the CMH test. If the Mantel Fleiss criterion is not satisfied the Fisher's exact test will be used instead of the CMH test to compare the two intervention groups.

For endpoints where any portion of the missing data is not imputed, but still needs to be accounted for under Missing at Random (MAR) assumptions, the **Generalized Linear Mixed Model (GLMM)** will be used (for more details see Section 6.13).

For subgroup analyses, a **logistic regression model** using data from all 3 intervention group will be used to obtain odds ratios and associated 95% CI. If any missing data were multiply imputed, the logistic regression model will be run on each of the imputation sets, and the odds ratios from each imputation set will have the log transformation applied before pooling across imputation sets. Once combined, the log transformed odds ratio and 95% CI will be back transformed to their original scale (Ratitch 2013) and presented. The treatment*subgroup interaction p-value will be obtained separately, based on logistic regression on the observed data and with only the data from the 2 intervention groups currently being analyzed fed into the model.

Continuous Efficacy Endpoints

For most continuous endpoints where any portion of the missing data is imputed using MI (see Section 6.11 for technical details), treatment comparisons will be performed using an **Analysis of Covariance (ANCOVA)** model on each of the imputation sets. The estimate of the mean change from baseline is the average of the mean change taken over all the MI data sets. The estimate of the variance of the mean change from baseline is the weighted sum of the average within-imputation variance and the between-imputation variance. The confidence interval for the mean change from baseline uses critical values from the t-distribution. The treatment difference between each guselkumab group versus the placebo group will be tested for each imputation dataset and then the analysis results across all imputation datasets will be combined. The treatment difference in the change from baseline is estimated by the average of the treatment differences over the MI data sets. The estimate of the variance of the treatment difference in the change from baseline is the weighted sum of the average within-imputation variance and the between-imputation variance, under the assumption of homogeneity of variance between intervention groups for performing ANCOVA within each imputation dataset. The confidence interval is based on the critical values from the t-distribution. The large number of observations in our data imply that the critical values from the t-distribution are almost identical to the critical values from the standard normal distribution.

The ANCOVA model will be based on the original scale and will include intervention group, baseline score, and randomization strata levels as the explanatory factors. The model will include data from all the 3 intervention groups.

For analyses where all missing data is imputed only a single time (e.g., change=0 for all missings) or not imputed with the missing assumed MCAR, treatment comparisons will generally be performed using ANCOVA.

For endpoints where any portion of the missing data is not imputed, but still needs to be accounted for under MAR assumptions, the **Mixed-Effect Model Repeated Measures (MMRM)** model will be used (for more details see Section 6.13).

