5.3.6. Other Efficacy Endpoints

In addition to the primary and key confirmatory secondary endpoints, other efficacy analyses related to reduction of signs and symptoms and physical function, skin disease, nail psoriasis, joint structural damage, and health related quality of life will be analyzed. These endpoints are NOT adjusted for multiplicity, and any p-values calculated will be considered nominal.

Treatment comparisons will ONLY be performed up to the Week 24 visit. Subsequent visits through Week 156 will be limited to descriptive summaries or model based estimates by study intervention.

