1. **Missing data for any reason** will be assumed to be MAR. The data is not explicitly imputed, but is accounted for in the analysis model.

Handling Rules for Missing Binary Data for Adjusted Composite Estimand

1. Missing data due to Natural Disaster (caused site closure, site access restrictions, or lockdowns) or Major Disruption will be assumed to be MAR. The data is not explicitly imputed, but is accounted for in the analysis model.
2. Missing data due to not entering LTE for reasons OTHER THAN lack of efficacy, worsening of PSA will be assumed to be MAR. The data is not explicitly imputed, but is accounted for in the analysis model.
3. Missing data for any other reason will be assumed to be MAR but conservatively imputed as NR

Analysis Testing for Adjusted Composite Estimand

Statistical comparison between a guselkumab group (100 mg q4w or 100 mg q8w) and the placebo group will be performed by visit through Week 24 using the Mixed-Effect Model Repeated Measures (MMRM) model for continuous endpoints and the Generalized Linear Mixed Model (GLMM) for binary response endpoints (see Section 6.13). No treatment comparison will be performed after Week 24. For continuous endpoints, only descriptive summaries and LSmeans by study intervention and visit will be presented after Week 24 through Week 156; for binary endpoints, only descriptive summaries and model based response rates by study intervention and visit will be presented after Week 24 through Week 156.

ICE Strategies for Treatment Policy Estimand

For the Treatment Policy Estimand, the occurrence of ICEs is considered irrelevant. This estimand looks at the effect of assignment to intervention group irrespective of changes to background PsA medications, study intervention adherence, or study retention.

Handling Rules for Missing Data for Treatment Policy Estimand

1. **Missing data for any reason** will not be imputed, assumed to be MCAR.

Analysis Testing for Treatment Policy Estimand

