A corresponding supportive analysis will be conducted using the Treatment Policy Estimand. For these analyses, the mFAS-UKR analysis set or further subset (if specified) will be used. For visits through Week 24, an ANCOVA model will be used for continuous endpoints, and the CMH test for treatment difference and 95% CI calculated based on Wald statistics will be used for the binary response endpoints. No treatment comparison will be performed after Week 24. For continuous endpoints, only descriptive summaries and LSmeans by study intervention and visit will be presented after Week 24 through Week 156; for binary endpoints, only descriptive summaries of response rates by study intervention and visit will be presented after Week 24 through Week 156.

Table 10 summarizes the analyses for supportive efficacy endpoints related to reduction of signs and symptoms and physical function, the methods for analyses, and the data handling rules used.

Table 10: Summary of Estimands, Analysis Sets, Data Handling Rules, and Analysis Methods for Endpoints of Signs & Symptoms and Physical Function

	Endpoint	Analysis Set	Missing Data Rules	Analysis Methods
ENDPOINTS BY VISIT THROUGH WEEK 24 AT WEEK-24 DBL, ADJUSTED COMPOSITE ESTIMAND				
1	Proportions of participants with ACR 20, ACR 50, and ACR 70 response	mFAS	NRI for MAR not due to Natural Disaster or Major Disruption	
 • Summarized descriptively • Response rates, and treatment difference in response rates and 95% CI and pvalue, based on GLMM

Table 10: Summary of Estimands, Analysis Sets, Data Handling Rules, and Analysis Methods for Endpoints of Signs & Symptoms and Physical Function

	Endpoint	Analysis Set	Missing Data Rules	Analysis Methods
2	ACR components	mFAS	-	
 Summarized descriptively LS mean (95% CI) for each intervention group
3	Change from baseline in ACR components	mFAS	-	
 Summarized descriptively LS mean (95% CI) for each intervention group
4	Percent change from baseline in ACR components	mFAS	-	
 Summarized descriptively LS mean (95% CI) for each intervention group
5	Change from baseline in HAQ-DI score	mFAS	-	
 Summarized descriptively LS mean (95% CI) for each intervention group, LS mean difference (95% CI) and p-values for differences between groups based on MMRM

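### SAP 5.3.1 names no interval to accompany Fisher's exact test in sparse binary tables, so the Wald interval stays by default and can undercover when the true rates differ

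*SAP*

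**What the plan says.** SAP 5.3.1, under Binary Response Efficacy Endpoints, treats analyses with single imputation or no imputation separately from those using multiple imputation. For the former it sets a CMH test and estimates the effect by the "difference in response rates between the guselkumab and placebo groups with a 95% confidence interval (CI) calculated based on Wald statistics". In describing the t-based interval for the multiply imputed case, it notes that this is one "which is different from the analysis not based on MI where normal distribution is used", so the non-imputed interval uses the normal critical value.

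A check for sparse data follows: "The Mantel Fleiss criterion will be used to determine the appropriateness of using the CMH test". The consequence is stated for the test only: "If the Mantel Fleiss criterion is not satisfied the Fisher's exact test will be used instead of the CMH test". The SAP does not say in terms that Wald is kept; it is silent on a replacement.

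SAP 5.3.6.2.10 shows where the rule applies. In the Treatment Policy analyses of Other Efficacy endpoints, missing data "will not be imputed, assumed to be MCAR", so the non-imputed paragraph governs. For visits through Week 24, "the CMH test for treatment difference and 95% CI calculated based on Wald statistics will be used for the binary response endpoints". The closing rows of Tables 10 to 13 repeat the Wald interval. SAP 5.3.6 adds that "any p-values calculated will be considered nominal".

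**The concern.** The Mantel-Fleiss criterion exists to flag tables whose counts are too small for a large-sample method. The SAP acts on it for the p-value and leaves the interval, which rests on the same kind of approximation, unchanged. In the Wald standard error an arm with no responders contributes zero variance, so the interval is too short exactly where the information is least.

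The endpoints most exposed are the demanding ones at early visits: ACR 70 and VLDA (Table 10), 100% PASI improvement (Table 11) and mNAPSI 100 (Table 12). The skin and nail endpoints are analysed in baseline-defined subsets, which reduces the counts further. At stake is whether an interval labelled 95% in these tables has roughly that coverage.

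**Working it through.** **Inputs.** Planned arm sizes are placebo 350, q8w 350 and q4w 250 (SAP section 3). The size of mFAS-UKR is not given, so planned sizes are assumed. The SAP prints no Mantel-Fleiss threshold; the usual value of 5 is assumed. The documents give no early-visit response rates, so the rates below are assumptions. The Wald interval is taken as unstratified.

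**The plan's own figure.** The documents state no coverage for the sparse-data rule. With the same arm sizes, the power above 99% in SAP Table 3 reproduces: the least favourable row (250/350, 55% vs 35%) gives 99.84%.

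**When the fallback applies.** With T responders in total, the Mantel-Fleiss quantity for a single sparse table is the smaller arm's share of T.
- 350/350: T/2 < 5, so it fails when T < 10.
- 250/350: T × 250/600 < 5, so it fails when T < 12.

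**One table worked through.** The Wald interval is d ± 1.96 × √(p1(1−p1)/n1 + p2(1−p2)/n2). For q8w 4/350 vs placebo 0/350:
- d = 4/350 = 1.143%
- SE = √(0.01143 × 0.98857/350 + 0) = 0.568%
- interval = 1.143% ± 1.114% = 0.03% to 2.26%
- Mantel-Fleiss quantity = 2.0, Fisher p = 0.124
- Newcombe interval = −0.15% to 2.90%

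With 0/350 vs 0/350 the standard error is zero and the Wald interval is (0, 0).

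**Exact coverage.** Both binomials were enumerated and the probability of every table whose interval contains the true difference was summed.

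| Arms | True rates | Wald coverage | Interval wholly below the true difference | All misses |
|---|---|---|---|---|
| 350/350 | 0.5% vs 0.1% | 82.5% | 17.3% | 17.5% |
| 350/350 | 1.0% vs 0.1% | 85.8% | 13.5% | 14.2% |
| 250/350 | 0.5% vs 0.05% | 71.3% | 28.6% | 28.7% |
| 250/350 | 1.5% vs 0.3% | 88.3% | 11.1% | 11.7% |

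Newcombe covers 97.8% to 99.8% in these four cases. Restricting to tables where Mantel-Fleiss fails leaves the Wald figures essentially unchanged (82.5%, 86.0%, 71.3%, 88.3%).

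**Where the misses come from.** At 0.5% vs 0.05% (250/350), the chance of no active responders is 0.995^250 = 28.6%, and every such table misses low. At 1.0% vs 0.1% (350/350), tables with 0 or 1 active responders miss low: 0.99^350 + 350 × 0.01 × 0.99^349 = 3.0% + 10.5% = 13.5%.

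**Wider range.** Over a grid of true rates from 0.05% to 2.0%, with the first-listed arm's rate at or above the other's and the criterion failing at least half the time, Wald coverage is below 95% at 82% of points for 350/350 (median 94.0%) and 95% of points for 250/350 (median 93.0%).

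**Equal rates.** Coverage is at least 95.3% at 350/350 (96.4% at 0.5% in both arms) and at least 94.2% at 250/350.

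**The case against.** The strongest reply is that the reach is small. These are supportive analyses with nominal p-values. The main analyses of the same endpoints use GLMM. The primary ACR 20 analysis uses multiple imputation, with design rates of 35% and 60%, far from sparse. Whether the criterion would ever fail is unknown. All of that stands.

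The four scenarios are also among the worse ones: the grid medians are only one to two points below nominal. The 71.3% case has about 1.4 responders expected in the whole comparison (250 × 0.005 + 350 × 0.0005 = 1.425), and the planned descriptive summaries would show an empty arm. That limits the harm but does not make the interval a 95% interval.

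A reader might infer something stronger: that Wald intervals excluding zero beside a Fisher p of 0.12 would produce spurious findings in favour of guselkumab. The numbers do not support this, for three reasons.
- The misses run the other way. Intervals lying below the true difference understate benefit. At equal rates of 0.1% to 1.0%, an interval excluding zero in guselkumab's favour occurs at most 2.3% of the time at 350/350 and 1.4% at 250/350.
- The mismatch at 4/350 vs 0/350 owes much to Fisher's conservatism. The uncorrected chi-square p is 0.045, and the Miettinen-Nurminen interval (0.05% to 2.90%) also excludes zero.
- At 250/350, tables with a non-significant Fisher test and a Wald interval excluding zero arise only when placebo has more responders, for example 0/250 vs 4/350 (p = 0.145).

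**Conclusion.** The gap is real and narrow. When the Mantel-Fleiss criterion fails, the SAP changes the test and leaves Wald as the only interval named. When the true rates differ, nominal 95% coverage can then fall to 82.5% to 85.8% at 350/350 and 71.3% to 88.3% at 250/350 under the assumed rates, mostly by placing the interval too low. When the rates are equal, coverage is about nominal or better.

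These sizes rest on a Mantel-Fleiss threshold of 5, an unstratified Wald interval, planned arm sizes and assumed rates. The SAP cites a source for its Wald method that is not part of the documents, and its multiply imputed counterpart is stratum-adjusted, so the exact figures could shift. The point concerns the accuracy of reported intervals in supportive tables. It gives no ground for doubting H1 to H4 or the main GLMM results.

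**What to change.** Add one sentence to SAP 5.3.1: when the Mantel-Fleiss criterion is not satisfied, the 95% CI for the difference in response rates is the Newcombe score interval instead of Wald. Apply it to the Treatment Policy analyses in Tables 10 to 13.

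This repairs coverage but does not force the interval to agree with Fisher's test. At 5/350 vs 0/350 (p = 0.062) Newcombe gives 0.07% to 3.30% and still excludes zero; at 7/350 vs 1/350 (p = 0.069) it does so again. Miettinen-Nurminen is the weaker choice for agreement, since it excludes zero even at 4/350 vs 0/350. If agreement is wanted, specify an exact interval matched to the test.

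The cost is one SAP sentence and one procedure option. The intervals become wider at visits with few responders: at 4/350 vs 0/350 the width goes from 2.26 − 0.03 = 2.23 to 2.90 + 0.15 = 3.05 percentage points.

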For change from baseline in modified vdH-S score, participants in each treatment group can be considered a mixture of two subpopulations: one subpopulation (Spop 1) with a change score of 0 regardless of treatment and another subpopulation (Spop2) with a change score sampled from a normal distribution. Therefore, the distribution of the modified vdH-S change scores is determined by 3 parameters: the probability that a participant has a change score of 0, the mean of the normal distribution, and the standard deviation (SD) of the normal distribution. The overall mean (ie, crude mean) of the change scores for a treatment group is the overall average of the change scores among all participants (including both Spops 1 and 2) in that treatment group.

In the PSA3002 study, the following statistics were observed for change from baseline in modified vdH-S score at Week 24 for each treatment group:

The overall mean (SD) of change from baseline in modified vdH-S score at Week 24 was 0.90 (3.14), 0.25 (2.52), and 0.45 (2.38) respectively, for the placebo, guselkumab 100 mg q4w, and guselkumab 100 mg q8w treatment groups. The assumptions for power calculations in this study are based in part on these data, adjusted for the difference in enrichment criteria between studies.

For this study, assuming an overall mean (SD) of change from baseline in modified vdH-S score as 1.13 (3.2), 0.25 (3.1), and 0.45 (3.1) respectively in the placebo, guselkumab 100 mg q4w, and guselkumab 100 mg q8w groups, a sample size of 350/250/350 participants (ie, 7:5:7 ratio, 950 in total) will provide a power of at least 90% and 80% to detect a significant treatment difference at a 2-sided significance level of $\alpha=0.05$ for guselkumab q4w vs placebo and guselkumab q8w vs placebo comparisons respectively.

Table 4 provides the statistical power for guselkumab 100mg q4w vs placebo under various assumptions, where the sample size is 250 in the guselkumab group and 350 in the placebo group.

Table 4: Statistical Power for Treatment Difference in Modified vdH-S Change from Baseline at Week24 for Guselkumab 100mg q4w vs Placebo (N=250, 350)

Percent Participant with extra 0 (Spop 1)	Normal Placebo (Spop 2)		Normal Guselkumab (Spop 2)		Overall Placebo		Overall Guselkumab		Overall Mean Difference	Power
	Mean	SD	Mean	SD	Mean	SD	Mean	SD		
15%	1.33	3.4	0.29	3.4	1.13	3.2	0.25	3.1	-0.88	92
15%	1.33	3.4	0.34	3.4	1.13	3.2	0.29	3.1	-0.84	89
15%	1.33	3.0	0.29	3.0	1.13	2.8	0.25	2.8	-0.88	96

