5.3.3. Analysis Specifications

5.3.3.1. Level of Significance

[figure not shown]
The overall type I error will be controlled among the primary and key confirmatory secondary endpoints at 5% as specified in Section 5.3.3.2.

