5.3.3.2. Multiplicity Adjustment for Testing Procedures

This study has 1 primary endpoint (proportion of participants who achieved an ACR 20 response at Week 24) and 1 key confirmatory secondary endpoint (change from baseline in modified vdH-S score at Week 24). With 2 treatment comparisons each, there are a total of 4 hypotheses to be tested. These hypotheses are explicitly listed in Section 2.

The overall Type I error of these 4 hypotheses will be controlled at a significance level of ≤ 0.05 . The testing procedure tests the primary and key confirmatory secondary endpoints, for the two regimens of guselkumab vs placebo, in a fixed sequence and each endpoint is tested at the two sided 0.05 level of significance. The fixed sequence testing method tests an endpoint only if the null hypotheses of no difference between the guselkumab regimen and placebo was rejected at the 0.05 level for all the endpoints above it in the sequence. This is shown visually in Figure 2 below.

Figure 2: Multiplicity Control

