5.3.5.1.3. Analysis Methods

The main analysis of the key confirmatory secondary endpoint will be analyzed at Week-24 DBL based on the Adjusted Treatment Policy Estimand.

In the primary efficacy analysis, data from all participants in mFAS(Section 4.2) will be analyzed according to randomized intervention group regardless of the treatment actually received.

ICE Strategies

For the Adjusted Treatment Policy Estimand, the treatment policy strategy will be used for ICEs 1 to 3, wherein all observed data collected for the endpoint is used. The occurrence of the intercurrent event is irrelevant: the value for the variable of interest is used regardless of whether or not the intercurrent event occurs.

The hypothetical strategy will be used for ICEs 4 and 5, wherein observed data collected after the ICE will not be used and will be assumed to be MAR, then imputed using FCS MI.

For participants experiencing multiple ICEs, an ICE in categories 4 and 5 will supersede an ICE in categories 1 to 3.

Handling Rules for Missing Data for Adjusted Treatment Policy Estimand

After ICE strategies have been implemented, remaining missing data will be handled as follows:

- **Missing data for any reason** will be imputed using FCS MI as described in Section 5.3.2.

Analysis Testing

Data from unscheduled visits which do not fit into the analysis window (Section 5.1.1.2) will not be used. Treatment comparisons for each imputation data set will be based on an ANCOVA model adjusted for baseline score and randomization strata levels. The analysis results from the N imputation datasets will be combined, according to Rubin (Rubin 1987), and the p-value for testing the treatment difference will be obtained.

In order to control the overall Type 1 error rate, the key confirmatory secondary endpoint will be tested in a fixed sequence if both hypotheses of the primary endpoint are statistically significant.

3. Guselkumab 100 mg q4w SC is superior to treatment with placebo SC as measured by change from baseline in modified vdH-S score at Week 24
4. Guselkumab 100 mg at Week 0, Week 4, then q8w SC is superior to treatment with placebo SC as measured by change from baseline in modified vdH-S score at Week 24.

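### The confirmatory vdH-S ANCOVA assumes one residual variance across three arms, the only observed SDs cited are unequal, and no planned analysis checks the assumption

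*SAP*

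**What the plan says.** SAP section 5.3.1 sets the general ANCOVA for multiply imputed continuous endpoints. It works on the original scale, and the variance of the treatment difference is obtained "under the assumption of homogeneity of variance between intervention groups for performing ANCOVA within each imputation dataset". The same section adds: "The model will include data from all the 3 intervention groups". SAP section 5.3.5.1.3 carries this to the key confirmatory secondary endpoint, where each comparison "will be based on an ANCOVA model adjusted for baseline score and randomization strata levels" and results are combined by Rubin's rules.

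SAP section 5.3.3.2 tests the four hypotheses "in a fixed sequence and each endpoint is tested at the two sided 0.05 level of significance". H3 (q4w) and H4 (q8w) on vdH-S come third and fourth.

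SAP section 3.1.2 reports that the mean (SD) Week 24 change in PSA3002 "was 0.90 (3.14), 0.25 (2.52), and 0.45 (2.38) respectively, for the placebo, guselkumab 100 mg q4w, and guselkumab 100 mg q8w treatment groups". It plans this trial on SDs of 3.2, 3.1 and 3.1, which it describes as based partly on PSA3002 and adjusted for different enrichment.

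SAP section 5.3.5.2 lists ten sensitivity analyses. They vary missing-data assumptions, analysis sets, trimming, covariates and radiograph windows, but all keep the same ANCOVA variance. The ANCOVA description in SAP section 6.13 offers no alternative.

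**The concern.** In PSA3002 the placebo variance was 3.14²/2.52² = 1.55 times the q4w variance and 3.14²/2.38² = 1.74 times the q8w variance. A three-arm model estimates one error variance from all participants. When the two active arms are less variable than placebo, they pull that estimate down, and it is then used for both comparisons with placebo. The standard errors come out too small, the intervals too narrow and the p-values too low.

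The third arm causes this. If each comparison pooled only its own two arms, the q8w standard error would be exact (equal group sizes) and the q4w one slightly conservative.

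At stake are the nominal level and interval coverage for two of the four confirmatory hypotheses, including the q8w structural-damage claim. Protocol section 2.1 says that claim did not reach significance in PSA3002.

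**Working it through.** **Inputs.** Arm sizes are 350 placebo, 250 q4w and 350 q8w; the SDs are those above (SAP section 3.1.2). The test is two-sided 0.05 (SAP section 5.3.3.2).

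**Plan's own figures first.** The planning mixture was simulated 10,000 times (15% zeros, normal SD 3.4 in both arms, ANOVA on van der Waerden scores). It gives power of 92.3% for q4w (SAP Table 4: 92) and 81.3% for q8w (SAP Table 5: 80). The stated power reproduces.

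**Formulas.**
- Pooled variance: s² = Σ(n−1)SD² / (950−3)
- Model SE = √[s²(1/n_T + 1/350)]
- True SE = √(SD_P²/350 + SD_T²/n_T)
- Actual error = 2[1 − Φ(1.96 × model SE / true SE)]; coverage is one minus this

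**PSA3002 SDs.** s² = (349×3.14² + 249×2.52² + 349×2.38²)/947 = 7.391, so s = 2.719.

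| Scenario (SD placebo/q4w/q8w) | Contrast | Model SE | True SE | Ratio | Error |
|---|---|---|---|---|---|
| PSA3002: 3.14/2.52/2.38 | q4w | 0.2251 | 0.2315 | 0.973 | 5.66% |
| PSA3002: 3.14/2.52/2.38 | q8w | 0.2055 | 0.2106 | 0.976 | 5.58% |
| Planning: 3.2/3.1/3.1 | q4w | 0.2598 | 0.2602 | 0.998 | 5.04% |
| Planning: 3.2/3.1/3.1 | q8w | 0.2372 | 0.2381 | 0.996 | 5.10% |
| q8w like placebo: 3.14/2.52/3.14 | q8w | 0.2260 | 0.2374 | 0.952 | 6.2% |

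**Simulation check.** With PSA3002 SDs and equal means, 40,000 three-arm trials per scenario (normal, and zero-inflated mixture) gave an error of 5.4 to 5.8% for q4w and 5.5% for q8w under pooling. With group-specific variances it was 4.9 to 5.1%. For the last row, 100,000 trials gave 6.3% pooled, against 5.1% with variances from the two compared arms only.

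**Role of the third arm.** With PSA3002 SDs, pooling placebo and q4w alone gives SE 0.2400 and an error of 4.2%. Pooling placebo and q8w alone gives 0.2106, which is exact.

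**Why the planning SDs are nearly equal.** Every row of SAP Tables 4 and 5 uses the same normal-component SD in both arms. In the base case the overall SD is √(0.85×3.4² + 0.85×0.15×m²), where m is the normal-component mean. This gives 3.17 for placebo (m = 1.33), 3.14 for q4w (m = 0.29) and 3.14 for q8w (m = 0.53). The gap comes only from the difference in means and vanishes when means are equal; the error is then 5.0%.

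**Power with group-specific variance, planning SDs.** q4w 92.3% (pooled 92.3%); q8w 81.5% (pooled 81.7%).

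**The case against.** The strongest reply is that the excess depends on PSA3002's SDs recurring, and the documents do not plan on that. PSA3002 required at least 5 swollen and 5 tender joints and CRP of at least 0.6 mg/dL (Protocol section 2.2.1.1.1). This trial requires 3 and 3, CRP of at least 0.3 mg/dL and at least 2 eroded joints (Protocol section 5.1). No PSA3002 arm sizes are given, so the precision of those SDs cannot be judged. They are also SDs of raw change, whereas the ANCOVA uses residual variance after adjustment for baseline and strata, which is not reported by arm. All of this stands.

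A second reply is that a type I error needs equal means, and if guselkumab does nothing the arms share one distribution and the error is 5%. This holds for the global null but does not dispose of H4. H4 is tested only after H3 succeeds, so its relevant null is that q4w works and q8w does not. There, placebo and q8w can be identical while a less variable q4w arm still lowers the shared error term, which gives the 6.2%. In that scenario the q4w comparison is conservative. Interval coverage does not need equal means at all.

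A third reply is that the effect is small. With PSA3002 SDs, only a q4w pooled p-value between about 0.044 and 0.050 would change its verdict. That is right, and it sets the severity.

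A reader might infer that the confirmatory test breaks its 5% claim. The documents do not support that: on the plan's own SDs the level is effectively nominal.

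**Conclusion.** The equal-variance assumption is stated by name, is at odds with the only observed SDs cited, and is not examined by any planned analysis. The consequence is conditional:
- About 5.6 to 5.7% error and 94.3 to 94.4% coverage if PSA3002-like SDs recur.
- About 6.2% for H4 if q4w keeps SD 2.52 and q8w behaves like placebo (SD 3.14).
- 5.0 to 5.1% with the planning SDs, and 5.0% with equal SDs.

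The calculations assume complete data at 350/250/350. They leave out covariate adjustment and between-imputation variance, and the documents give no missing-data rate from which to gauge the latter. The SAP's enrichment adjustment may justify the higher planning SDs, but it gives no reason why enrichment would remove the difference between arms. This is a cheap improvement of minor severity; it is not an established error in the plan.

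**What to change.** In SAP sections 5.3.1 and 5.3.5.1.3, keep the ANCOVA mean model (arm, baseline score, strata; three arms) but drop the common-variance assumption. Within each imputation, either allow arm-specific residual variances with Satterthwaite or Kenward-Roger degrees of freedom, or use HC3 standard errors, and then pool by Rubin's rules. HC3 leaves the point estimate unchanged; arm-specific variances may shift it slightly through the weighting of the covariates. Name one option in advance.

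If the sponsor prefers to keep the main analysis, the minimum is to add this as a further sensitivity analysis for both H3 and H4 in SAP section 5.3.5.2 and Table 8.

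The cost is one sentence and one model option. If PSA3002 variances recur, standard errors rise by about 2.8% for q4w (0.2315/0.2251) and 2.5% for q8w (0.2106/0.2055). Under the planning SDs the loss of power is at most 0.2 points.
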